## **10. Study Objectives/Aims:**

*Aim 1:* To pilot the ***Shauriana*** intervention among 10 participants for 3 months, in order to ensure that intervention and study procedures are optimized.

*Aim 2:* To determine the acceptability, feasibility, and safety of the ***Shauriana*** intervention and estimate initial effect size compared to standard care on PrEP uptake and adherence assessed by drug levels over 6 months in a pilot randomized controlled trial (RCT).

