**Table 1. Overview of Participant Enrolment**

Stage	Pilot Test (Aim 1)	Feasibility RCT (Aim 2)
Purpose	Standardization of intervention	Initial testing of feasibility, tolerability, acceptability, and safety; estimate of effect size
Group	10 HIV-negative GBMSM participants	60 HIV-negative GBMSM participants

**Eligibility Screening.** A brief permission script will be used to confirm consent for screening. Basic sociodemographic data (age, sex), a brief risk behavior assessment, and reasons for screening out or failing to enroll will be noted. Men who are found to be ineligible will be referred by *Anza Mapema* staff to HIV prevention or care programming as indicated, including risk reduction counseling, condoms and lubricants, STI screening and treatment, programmatic PrEP if eligible and interested, and HIV care for men who self-report as HIV-positive. Men who are eligible will undergo an informed consent process as described in section 12 (Ethical Considerations).

**Inclusion criteria:** Men recruited for each study aim must meet all of the following criteria:

- Biologically male at birth and identifies as male, according to self-report
- 18 to 35 years of age
- Resident in the Kisumu area for  $\geq 12$  months
- Reports anal intercourse with a man in the past 3 months
- Not currently taking PrEP for HIV prevention in the past 3 months
- Willing to provide complete locator information
- Willing to undergo all study procedures, including HIV testing and counselling
- Not currently participating in any HIV prevention or vaccine study
- Planning to remain in the study area for at least 6 months

*For the pilot study only, men will be required to speak English, in order to expedite the study team's analysis of feedback from these participants in preparation for the RCT. Of note, approximately 50%-60% of young MSM in Kisumu speak English.*

**Exclusion criteria:** Men who meet any of the following criteria will be excluded from this study:

- Unable to understand the study purpose and procedures
- Unwilling to adhere to study procedures

- Currently under the influence of alcohol or drugs
- Prior diagnosis of HIV infection

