Trial enrollment and randomization. Once consent has been given, participants will be randomized to a study arm. The process of randomization to one of two study arms will be explained carefully and reviewed as part of the informed consent process. Computer-generated randomization will be used to assign participants in a 1:1 ratio to the standard care or intervention group, in blocks of 4, to ensure that equal numbers are randomized across arms. Numbered envelopes indicating the assignment will be prepared in and sealed by the UW CFAR Biometrics Core; study staff will not be aware of an individual's condition until the envelope is opened.

Clinic visits. Consistent with the latest Kenyan guidelines, all trial field-test participants will undergo study procedures at baseline, month 1, month 3, and month 6 at the **Anza Mapema** clinic. As for the pilot study, clinic visits will include HIV counselling and testing, screening for STI symptoms, and individual counselling about HIV prevention methods, including standard of care counselling (information, risk reduction, and PrEP counselling). A standardized physical exam will be performed at each visit, and both blood and urine samples will be collected. For participants taking PrEP, medical history will also focus on PrEP side effects and seroconversion symptoms, and PrEP refills will be provided (monthly for the first 3 months then quarterly). After completing these procedures, RCT participants will complete a detailed ACASI described below. Each of the four clinic visits (baseline, month 1, month 3, and month 6) will take from 1.5 to 2 hours; participants will be reimbursed KSh 500 for each clinic visit.

Standard care. All participants will receive standard care at the *Anza Mapema* Clinic, including standard counseling as described above; screening for depressive symptoms and substance use disorder; monthly *Anza Mapema* peer outreach for education and supply of condoms and lubricants; support group meetings; and social events as described above under “Previous Studies and Rationale.” Attendance at *Anza Mapema* support groups and social events by *Shauriana* study participants will be tracked, as will the content of these group and social events during the study period. To ensure fidelity of delivery for each arm, we will review study progress, procedures, and emergent issues at weekly study meetings.

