Exit interviews. At study completion or any visit on which a participant withdraws, an exit interview will be conducted regarding experiences, including any social harms of participation and feedback on standard care or the *Shauriana* intervention. Exit interviews will be conducted by the *Shauriana* Project Research Coordinator, who is based at NYARWEK, using a semi-structured exit interview guide. Notes will be taken and interviews will be recorded using a digital recorder. All participants who complete an exit interview will receive KSh 500 as reimbursement for their time and transport. The topic guide for the exit interviews is included in “[Appendix E: Shauriana Exit Interview Guide](#).”

Schedule of procedures. A table summarizing procedures for the Shauriana study is included in “[Appendix G: Schedule of Procedures](#).”

Power considerations. This project is designed to develop a novel intervention to promote PrEP adherence and sexual health among African GBMSM and to assess its acceptability, feasibility, and safety in a clinical trial setting. It is not designed or powered to determine the overall intervention effect nor the effects of individual components of the intervention. Data on PrEP drug levels and other secondary outcomes in each study arm will help to evaluate whether the intervention is at least as good as standard care and provide some insight into the promise of the intervention to inform larger-scale testing. See Section 13 for statistical analysis plans.

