the ***Shauriana*** intervention. RCT participants will be followed for 6 months total, attending visits as detailed in the protocol. At each clinic visit, participants will be given 500 Kenyan shillings (about \$5) to reimburse them for their time and transport expenses. RCT participants will be reimbursed 350 KSh for their transportation after receiving each of the four core ***Shauriana*** modules, as participants may need to travel to a safe space for intervention delivery to ensure privacy.

Men who test positive for HIV during the study will be withdrawn from the trial and referred to care at the comprehensive care clinic of their choice, either at the ***Anza Mapema*** Clinic run by the Nyanza Reproductive Health Society (NRHS) or at any of several other clinics providing HIV care and treatment in the greater Kisumu area. All non-scheduled contacts with study staff will be documented. At month 6 or at the time of withdrawal for any reason (e.g., a move from the study area), a semi-structured exit interview will be conducted regarding experiences, including any social harms of study participation. Permission will be requested for digital recording of the semi-structured exit interviews during the consenting process, and confirmed at the time of the interview. Men will be reimbursed KSh 500 for completing their exit interview.

***Research Material Obtained from Participants:*** At study visits, detailed audio computer-assisted self-interview (ACASI) data collected will include sociodemographic background; sexual risk behavior; experience of stigma, discrimination and violence; depression; alcohol and drug use; current physical symptoms; and HIV and PrEP knowledge. Before each PrEP dispensation/refill, data on PrEP status and adherence will also be recorded by ACASI. Names will be included only on a registration form containing information to be used in locating the participant in case of need (e.g., laboratory results requiring follow-up, tracing after a missed visit); this registration form will also be used to prevent duplicate enrolments. Names will not be included in routine data collection forms or in the computer database. Names of sexual contacts will not be collected.

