approaches will help assess the utility of the instruments used for future analyses and research in HIV-negative Kenyan GBMSM.

Given the preliminary nature of this work and the small sample size dictated by time and budget limitations, secondary analyses will focus on obtaining estimates of Table 2 secondary outcomes (PrEP uptake, adherence, refills, and drug levels) in each group and characteristics associated with these outcomes, for use in design of a larger study. Retention will be compared across study arms using uncorrected Chi square tests in an intent-to-treat analysis. Rates and patterns of self-reported PrEP adherence (defined as taking 4 or more doses per week) will be examined, and assessment methods will be compared using bivariate analyses (e.g., Spearman correlation coefficients for continuous variables). Sociodemographic and other potential cofactors will be evaluated for associations with adherence measures and other outcomes (e.g., urine TFV levels, dried blood spot TFV-DP) using Wilcoxon rank sum or independent-sample t tests, Spearman or Pearson correlations, and chi-square tests as appropriate. Multivariable analyses will adjust for sociodemographic and other potential cofactors. Parsimonious model testing will explore potential intervention efficacy.

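### Does the plan leave open whether PrEP drug levels are estimated in all randomised men or only in men on PrEP, and which measure counts as adherence?

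*Combined protocol and SAP*

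**What the plan says.** Section 10 sets Aim 2 as estimating an initial effect "on PrEP uptake and adherence assessed by drug levels over 6 months". In section 11, Table 2 lists four secondary outcomes in separate rows: PrEP uptake, PrEP adherence (self-report by ACASI), PrEP refills and PrEP drug levels (urine TFV, plus dried blood spots if funded). The power paragraph of section 11 states that the trial is not powered for an intervention effect, and adds: "Data on PrEP drug levels and other secondary outcomes in each study arm will help to evaluate" whether the intervention does at least as well as standard care.

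Section 13 says that "secondary analyses will focus on obtaining estimates of Table 2 secondary outcomes (PrEP uptake, adherence, refills, and drug levels) in each group". On adherence it says "Rates and patterns of self-reported PrEP adherence (defined as taking 4 or more doses per week) will be examined", and the same sentence goes on to plan bivariate comparisons of the assessment methods. An analysis set is named only once: "Retention will be compared across study arms using uncorrected Chi square tests in an intent-to-treat analysis".

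An inclusion criterion in section 11 is "Not currently taking PrEP for HIV prevention in the past 3 months". At RCT clinic visits "both blood and urine samples will be collected". Section 12 adds: "Before each PrEP dispensation/refill, data on PrEP status and adherence will also be recorded by ACASI".

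**The concern.** Two things look unsettled.

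The first is the denominator. Men are off PrEP at entry, so starting it happens after randomisation, and uptake is something the intervention tries to change. If drug levels were summarised only in men on PrEP, the arms would be compared on groups selected by a post-randomisation event. An intervention that drew in hesitant men who took PrEP less well could look worse among starters while doing better across everyone randomised. Since intent-to-treat is attached to retention alone, and section 12 ties some adherence data to dispensing, a reader could wonder which population is meant.

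The second is the label. Aim 2 speaks of adherence by drug level, whereas Table 2 and the single threshold in section 13 attach the word to self-report. In the team's earlier PrEP cohort (section 8) the two were far apart: median self-rated adherence was 98%, while drug was undetectable at 178 of 275 visits and at a protective level at 28.

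At stake would be the estimate carried into the design of a larger trial, which section 13 gives as the purpose of these analyses.

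**Working it through.** The documents give no power, alpha or effect size behind the 60 men, so there is no design figure to reproduce. The check has two parts: reading the text, and sizing the gap.

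**Text on drug levels**
- Section 13 estimates them by group, and the power paragraph of section 11 by study arm.
- Section 11 (Clinic visits) collects urine at RCT visits with no PrEP condition.
- Sections 11 (Laboratory testing) and 12 store samples from baseline, month 3 and month 6. Men are off PrEP at baseline, so sampling cannot be tied to PrEP use.
- Section 11 (Aim 2 Procedures) commits to testing urine and does not limit this to users.
- Section 11 (Standard care) keeps men who stop PrEP in follow-up.

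The section 12 sentence about dispensing and refills concerns ACASI self-report. It says nothing about drug levels. No statement on drug levels supports a users-only analysis.

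**Size of the gap (illustrative)**

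Inputs:
- Detection among starters: (275 − 178)/275 = 97/275 = 35.3% (section 8). This is dried-blood-spot TFV-DP standing in for urine TFV.
- Control uptake: 112/(112 + 49) = 112/161 = 69.6% (section 7, first offer).
- Men who do not start have no drug.

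Control detection in all randomised men = uptake × detection among starters = 0.696 × 0.353 = 24.5%. The gap is 35.3 − 24.5 = 10.7 points (from unrounded values).

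Section 7 also reports that 11 of the 49 who declined accepted later. Uptake is then (112 + 11)/161 = 123/161 = 76.4%, all-randomised detection is 0.764 × 0.353 = 26.9%, and the gap is 8.3 points.

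**Can the two readings disagree in sign?** Suppose the intervention adds 20 points of uptake to 69.6%, in men whose detection is d.
- Difference in all randomised men = 0.20 × d.
- Difference among starters = (0.2454 + 0.20 × d)/0.8957 − 0.3527.

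| d | All randomised | Starters |
|---|---|---|
| 10% | +2.0 points | −5.6 points |
| 20% | +4.0 points | −3.4 points |
| 35.3% | +7.1 points | 0 |

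A reversal needs the added men to have clearly lower detection. With equal detection there is none.

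**Precision.** The 95% half-width for a difference is 1.96 × √(2p(1 − p)/n).
- All randomised, p = 0.245, n = 30: 21.8 points.
- Starters, p = 0.353, n = 30 × 0.696 = 20.9: 29.0 points.

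**Consequence for a later trial.** For a 1.5-fold increase with 80% power and two-sided 5%:
- From 35.3%: 124 starters per arm, or 124/0.696 ≈ 178 randomised.
- From 24.5%: 221 randomised.

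The like-for-like contrast is therefore about 178 against 221 per arm. At 76.4% uptake it is 124/0.764 ≈ 162 against 192. A 1.5-fold rise is also a different absolute effect on each base.

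**Weakness of the 35.3% input.** It is a proportion of visits (275 visits, 161 men), in a cohort where everyone was offered PrEP. Section 8 does not say that all of them started. If non-starters are among those visits, multiplying by uptake counts non-uptake twice. Detection among starters would instead be about 0.353/0.696 = 51%.

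**The case for a change.** The best argument for acting is that collecting a sample is not an analysis rule. Section 13 never says how men who never start, or who stop, are counted, and it reserves intent-to-treat for retention. The by-arm estimate is the deliverable here, so its population could be fixed before data are seen, at the cost of a sentence and no new sample. If the 35.3% already includes non-starters, the gap between the readings would be wider than shown: about 51% against 35.3%.

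The omission is real, and the size of the gap is uncertain in both directions. It does not follow that the plan would yield a wrong result. A users-only analysis would need a restriction that appears nowhere in the drug-level text. An analyst working from that text would include every sampled man in his randomised arm.

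On the label, the distance between self-report and drug level in the earlier cohort is a good reason not to let one replace the other, and the plan does not do so. Table 2 and section 13 keep both as separate outcomes, the measures are to be compared with each other, and the section 13 threshold is openly described as self-reported. Aim 2 itself names drug levels, so a reader knows which row answers it.

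There is also some inconsistency over dried blood spots. Testing depends on funding in section 11 (Aim 2 Procedures, Table 2 and the start of Laboratory testing), but later in Laboratory testing and in section 14 it is written without that condition. This is clerical: the condition is stated earlier in the same subsection, and section 14 describes shipping.

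**Conclusion.** No change to the plan is needed. The missing analysis set is a detail that the surrounding text fills: drug levels by arm, in all randomised men with a sample, beside uptake. The label is a loose use of one word across two separately listed outcomes and alters no estimate.

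Under the illustrative inputs the two denominators differ by about 8 to 11 points in the control arm, and they disagree in sign only if the added starters have much lower detection. These figures rest on dried-blood-spot results standing in for urine, a visit-level proportion, uptake borrowed from a coastal programme, and no drug in non-starters. They compare with half-widths of about 22 to 29 points at 30 men per arm, in a trial whose primary outcomes are acceptability, feasibility and safety and which disclaims power for effect. The conclusion would be different if any passage limited urine testing or drug-level estimates to PrEP users. None does.

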#### **14. Laboratory Specimens and Biohazard Containment:**

***Laboratory Specimens:*** The following specimens will be collected for the tests to be conducted for the randomized trial:

- Blood (15 milliliters) for creatinine and hepatitis B surface antigen testing at baseline and dried blood spots plus storage at baseline, month 3, and month 6
- Urine (10 milliliters) for PrEP drug level testing

Research staff will adhere to standards of good clinical laboratory practice, and local SOPs for specimen management, including proper collection, processing, labeling, and transport of specimens to the CDC-KEMRI laboratory for testing or the UNIM Research and Training Centre for storage.

***Biohazard Containment:*** Transmission of HIV and other blood borne pathogens can occur through contact with contaminated needles, blood, and blood products. Appropriate blood and secretion precautions will be employed by all personnel in the collection of clinical samples and the shipping and handling of all clinical samples and isolates for this study, as currently recommended by the World Health Organization and the Kenyan Ministry of Health. After all requisite permissions are obtained, urine and dried blood spot samples will be shipped to [name] at the University of Washington and then forwarded to Molecular Testing Labs in Vancouver, Washington, USA, for PrEP drug level testing. All specimens will be shipped using packaging that meets requirements specified by the International Air Transport Association Dangerous Good Regulations for UN 3373, Biological Substance, Category B, and Packing Instruction 650. In addition, all infectious specimens will be transported in accordance with United States regulations (42 CFR 72).

#### **15. Study Limitations/Possible Complications and How to Minimize Them:**

This proposal includes an ambitious research plan and timeline, based on the urgency of the problem addressed. We acknowledge several potential complications:

1. Research involving GBMSM in Kenya can be sensitive, and a good relationship with the key stakeholders (e.g., Ministry of Health, police, media) will be critical to ensure safety. While male-male sex is illegal in Kenya, the Kenyan courts recently ruled against forced

anal examinations at police stations. We have safely conducted multiple studies with GBMSM participants in Kenya since 2005, and have taken measures in Kisumu to ensure we have assistance should any problems arise (e.g., the *Anza Mapema* CAB has successfully resolved sensitive situations through dialogue). In addition, security is a pillar of NYARWEK's work, and includes GBMSM sensitivity training for local police and judiciary. We also have the endorsement of the Kisumu County Ministry of Health for the proposed work, and confer with County Health officials periodically and when issues arise.

2. We do not anticipate that recruiting and retaining participants for the Aim 1 pilot and the Aim 2 trial will be difficult. The >600 HIV-negative participants recruited and high retention achieved in *Anza Mapema*, support from GBMSM partners, and a strong community outreach program suggests recruitment of 60 GBMSM participants not currently taking PrEP will not be challenging.
3. Because we will conduct the intervention trial in a single community with overlap in social and sexual networks, there could be contamination of arms, with participants in the standard care arm receiving some intervention components. We will address this risk by locating all intervention procedures outside the *Anza Mapema* Clinic, monitoring standard care at the *Anza Mapema* Clinic, and strict adherence to trial protocols. We had success with such monitoring in the *Shikamana* trial, in which audits of recorded counseling sessions found minimal contamination of standard vs. intervention approaches. Manipulation checks will also be included in exit surveys to identify potential crossover contamination.
4. We also acknowledge that there may be differences in attention due to increased peer contact or counseling efforts in the intervention arm. We will monitor data on *Anza Mapema* Clinic visits (planned study visits and interim visits), *Anza Mapema* social activities, and all *Shauriana* intervention contacts with participants, to assess differences in attention across study arms.
5. Finally, the HIV prevention landscape is constantly changing and injectable PrEP may be on the horizon. Even if injectable PrEP replaces oral PrEP and reduces the burden on participants to adhere to daily therapy, GBMSM in Kenya and other rights-constrained settings will continue to face stigma and discrimination that may affect uptake and maintenance of HIV prevention. Hence, a holistic approach to sexual health such as that provided by the *Shauriana* intervention would still be pertinent and needed.

## **16. Timeline/Time Frame:**

Aims 1 and 2 of the project (pilot phase and trial of the *Shauriana* intervention) will occur over an 18-month period, from the time all ethical approvals are in place. Piloting will take place in months 1-5 of the proposed work, after training of the peer facilitators and of the *Anza Mapema* Clinic staff on the research protocol. Recruitment for the RCT would take place over months 6-12, with 6-month follow-up for each enrolled participant. As work progresses, we will present abstracts at international and national conferences and submit manuscripts to top-tier journals with an audience inside and outside of Africa.

